### 8.3.3 Dose Modifications

#### Part A

No dose reductions are permitted in Part A. If a subject experiences a DLT during Cycle 1, the subject should be discontinued from the study.

At the end of Part A, if the subject is receiving a sub-MTD dose, the dose may be escalated to the MTD in consultation with the Medical Monitor and Sponsor.

If a subject experiences an AE meeting DLT criteria after Cycle 1, dosing with ASN002 will be interrupted. If the AE resolves within 7 days to CTCAE grade  $\leq 1$ , the subject may resume dose administration at the same dose or at a lower dose level as agreed between the sponsor and investigator. If the AE does not resolve to CTCAE grade  $\leq 1$  within 7 days or if the DLT reoccurs, the subject must be discontinued from the study.

**Part B**

During Part B of the study, dose interruption (of up to 7 days) and modification for an AE meeting the criteria for DLT is allowed. For a drug-related toxicity, the dose should be immediately interrupted and supportive care provided until the AE resolves to  $\leq$  Grade 1. After the AE resolves to  $\leq$  Grade 1, retreatment at a lower dose may be considered upon agreement between the investigator and Sponsor medical monitor. If the toxicity recurs after re-challenge at a lower dose, study treatment should be discontinued. In the absence of  $>$  Grade 1 drug-related toxicity after at least 4 weeks of study treatment, subjects may be considered for intra-patient escalation to a higher dose that has been declared safe, in agreement with the investigators and Sponsor. The decision on possible escalation to a higher dose will be made on a case by case basis.

Guidelines for dose modification for patients starting at 75 mg BID are listed in **Table 7**.

**Table 7: Dose Modifications for Part B**

Dose Level	mg (BID)
-1	50
Recommended dose	75
+1	100

#### **8.4 Study Drug Administration**

ASN002 will be provided as 5-mg, 20-mg, and 50-mg tablets for oral administration. All study medication supplies will be provided by Asana BioSciences, LLC. The subject should be instructed to take the study drug at the same time, either once or twice daily.

All study drugs will be administered orally every 12 or 24 hours, as assigned, on an empty stomach (either 1 hour before or 2 hours after a meal or snack) with approximately 240 mL of water (unless the patient is participating in a cohort in which co-administration with food is required). On study days in which there is a single PK sample, the subject should fast for at least 2 hours prior to collection of the PK sample. On study days with multiple PK samples, the subject should fast overnight (at least 8 hours prior to study drug administration) and remain fasting for 2 hours after study drug administration. The date and time of the dose(s) taken prior to or on PK sampling days will be collected by the study site or via a diary card provided to the subject.

Subjects receiving the twice daily dosing schedule will receive a single dose on Day 1 and skip the evening dose. On Day 2, twice daily dosing cohorts will begin twice daily dosing. Subjects assigned to the once daily dosing schedule will have a single dose on Day 1 and will skip the Day 2 dose. All other Day 2 study procedures should be completed per protocol except study

drug dosing. On Day 3, subjects assigned to once daily dosing will begin continuous once daily dosing. The effect of co-administration of ASN002 with a meal may be evaluated. Patients enrolling in this cohort will take their medication immediately after a meal

#### **8.4.1 Missed or Vomited Doses**

Should the subject forget to take the study drug, s/he should take the study drug as soon as s/he remembers up to 2 hours after the planned dosing time. Thereafter, the forgotten dose should not be taken. Vomited doses should not be retaken.

#### **8.4.2 Duration of Treatment**

The subject may continue to receive treatment with ASN002 in the absence of progressive disease or intolerable toxicity for up to 12 months.

Further details regarding the study drug can be found in Section **16**

### **8.5 Procedures and Criteria for Dose Escalation**

#### **8.5.1 Safety Review Committee**

The safety review committee will decide whether the dose escalation will continue to the next planned (or intermediate) dose level, if additional subjects will be added to the current dose level or if the dose escalation will be stopped. The safety review committee can also terminate the study due to safety concerns. Each review will be conducted with the latest available data.

The overall safety will be evaluated after each cohort based on the safety data from the first 28 days of treatment. The safety data will include medical history, all AEs, concomitant medications, vital signs, electrocardiogram (ECG) findings, and laboratory data.

The safety review committee will be comprised of the following members: sponsor representatives including the clinical pharmacologist, medical adviser, chief medical officer, clinical manager; site investigators from active sites; CRO representatives including the medical monitor, pharmacovigilance medical monitor. Other representatives may be included as needed.

#### **8.5.2 Dose Escalation Criteria**

Dose escalation will continue until the MTD, a plateau of ASN002 plasma concentration has been identified, or until the planned highest dose level is reached (refer to section **8.3.1**).

Initially, 3 subjects will be treated at the same dose level. There will be at least a 24-hour interval between the administrations of the first dose of the study drug for each subject.

After a minimum of 3 subjects in each cohort have completed cycle 1 of treatment and the safety review has been performed, 3 new subjects can be enrolled at the next higher dose level, in the absence of DLT. No intra-subject dose escalation is permitted during the dose escalation phase.

If 1 of the first 3 subjects experiences a DLT, an additional 3 subjects will be enrolled at the same dose level. The dose escalation will be stopped if 2 or more subjects among a cohort of 3 or 6 subjects experience a DLT. Three additional subjects will be entered to the previous lower dose level cohort, if only 3 subjects were treated in that cohort.

The MTD is defined as a dose level immediately below that at which  $\geq 2$  of 6 subjects experience a DLT. Subjects considered to be evaluable for the MTD determination are the subjects who have received the study drug for 28 days or who have discontinued the study drug earlier than 28 days because of a DLT.

Dose escalation can also be stopped based on the PK data if a plateau in ASN002 plasma concentration versus the dose curve is observed prior to reaching the MTD. Subsequent development decisions regarding the therapeutic doses of ASN002 for future studies will be considered in the evaluation of PK data.

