The study design includes a screening period (up to 28 days), and a DLT observation period of 28 days (Cycle 1). A subject with no DLTs during Cycle 1 will have the opportunity to continue to receive ASN002, at the discretion of the investigator. Subjects that are not able to complete Cycle 1 for reasons other than DLT will be replaced. Subjects participating in Parts B who discontinue from the study due to non-compliance or protocol violations may be replaced at the discretion of the Sponsor. Subjects may receive treatment with ASN002 in the absence of intolerable toxicity or disease progression for up to 12 months. If the subject is not a candidate for or chooses not to participate in additional treatment cycles, an end of treatment visit will be performed. A follow-up visit will be performed at least 30 days after the last dose of study medication.

In Part A of the study, after the Safety Review Committee (SRC) has met and agreed to dose escalation, up to 3 additional subjects may be allowed in a lower cohort to gather additional PK, PD and safety data. The inclusion of these subjects will be based on agreement with members of the SRC and the Sponsor.

Part B will be an expansion of the MTD cohort into 6 disease-specific groups to evaluate preliminary clinical anti-tumor activity. Each cohort will contain up to 14 subjects with DLBCL,

MCL, FL, PTCL, MF, and CLL. Subjects may receive treatment with ASN002 in the absence of intolerable toxicity or disease progression for up to 12 months.

The study design is illustrated in **Figure A**. The Schedule of Assessments for all parts of the study is located in **Table 1** and **Table 2**.

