### 8.5.3 Dose-Limiting Toxicity (DLT) Definitions

During Phase 1, the MTD will be determined based on DLT occurring during the first 28 days plus any rest period if applicable (i.e. Cycle 1). All adverse events unless they have been determined to be not related to study drug will be taken into consideration in determining DLT. NCI-CTCAE version 4.03 will be the basis for the descriptive terminology and grading of adverse events. DLT are defined as follows:

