### 9.3.1 Replacement Procedures

During Part A, a subject who prematurely discontinues from the study before completing 28 days of the dose escalation component for reasons other than DLT, or has demonstrated significant non-compliance with ASN002 dosing, may be replaced at the discretion of the sponsor. Subjects participating in Parts B who discontinue from the study due to non-compliance or protocol violations may be replaced at the discretion of the Sponsor.

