#### **Hematologic DLT**

- A grade  $\geq 4$  neutropenia or thrombocytopenia that lasts more than 7 days after the last dose of study drug;
- Febrile neutropenia;
- A grade  $\geq 3$  thrombocytopenia in the presence of bleeding.

If one of the first 3 patients treated at a given dose level develops a DLT, up to 3 additional patients are to be treated at that dose level. If at least 2 patients treated at a given dose level develop DLT, dose escalation is to be stopped, and the penultimate dose level will be considered the MTD.

The MTD is defined as a dose level immediately below that at which  $\geq 2$  of 6 subjects experience a DLT. Subjects considered to be evaluable for the MTD determination are the subjects who have received the study drug for 28 days or who have discontinued the study drug earlier than 28 days because of a DLT.

The safety evaluations used to define tolerability and determine DLTs will include the following:

- Adverse events (AEs), monitored from the time the subject signs the consent form until 30 days after the last dose of ASN002;
- Prior, concomitant, and post medication use;
- Extent of exposure to study drug;
- Study drug compliance;
- Clinical laboratory tests (hematology, lipid panel, liver function, comprehensive metabolic panel, urinalysis, pregnancy [if applicable]);
- Vital signs;
- 12-lead Electrocardiogram (ECG);
- Physical examination.

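### Read literally, the MTD-evaluability sentence leaves out a Cycle 1 DLT that follows a stop for another reason, in conflict with the plan's own DLT-counting and replacement rules

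*Protocol*

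**What the plan says.** **Evaluability.** Protocol 8.5.2 admits to the MTD determination only subjects "who have received the study drug for 28 days or who have discontinued the study drug earlier than 28 days because of a DLT". SAP 2.3.2, under its hematologic DLT heading, repeats the rule: "Subjects considered to be evaluable for the MTD determination are the subjects who have received the study drug for 28 days", or who "discontinued the study drug earlier than 28 days because of a DLT". Neither document has a third category.

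**DLT window.** Protocol 8.5.3 says that "the MTD will be determined based on DLT occurring during the first 28 days plus any rest period if applicable (i.e. Cycle 1"). It adds: "All adverse events unless they have been determined to be not related to study drug will be taken into consideration in determining DLT". Neither statement depends on the subject still taking drug or on why drug was stopped.

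**Counting.** In Protocol 8.5.2, "The dose escalation will be stopped if 2 or more subjects among a cohort of 3 or 6 subjects experience a DLT". The word is subjects, not evaluable subjects. SAP 2.3.2 stops escalation and fixes the MTD once at least two patients treated at a level have a DLT. The MTD definition in the Protocol synopsis (Safety Analyses) counts subjects with DLTs in the first 28 days.

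**Replacement.** Protocol 8.1 says "Subjects that are not able to complete Cycle 1 for reasons other than DLT will be replaced", and SAP 3.1 agrees. Protocol 9.3.1 says that a Part A subject who leaves before completing 28 days "for reasons other than DLT, or has demonstrated significant non-compliance with ASN002 dosing, may be replaced at the discretion of the sponsor".

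**The concern.** One rule classifies subjects by why they stopped drug. The others classify events by when they occurred. The two approaches disagree for a subject who stops in Cycle 1 for progression, intercurrent illness or a Grade 2 event, and then has a Grade 3 or higher event, not judged unrelated, before Day 28. By the evaluability sentence that subject has neither 28 days of drug nor a stop caused by a DLT, so drops out of the MTD set and, under 8.1, is replaced. By 8.5.3 and the stopping rules the same event counts.

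In a 3+3 design a single event can decide between escalating, expanding and stopping. Leaving out only events, and then giving the slot to a new subject, can move the decision in one direction only: upward. The MTD is a Part A primary objective, so its counting rule should have one reading.

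**Working it through.** **1. The passages applied to one subject.** Drug is stopped on Day 12 for progression; a qualifying event, not judged unrelated, occurs on Day 20.

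| Rule | Event counted? |
|---|---|
| Protocol 8.5.2 and SAP 2.3.2, evaluability sentence | No: neither condition is met |
| Protocol 8.5.3, DLT window | Yes |
| Protocol 8.5.2, stopping rule | Yes |
| SAP 2.3.2, DLTs among treated patients | Yes |
| Protocol synopsis, MTD definition | Yes |
| Protocol 8.1 and SAP 3.1, replacement | Subject must be replaced |
| Protocol 9.3.1, replacement | Subject may be replaced |

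The opening of Protocol section 15 gives the SAP priority where the two documents differ. That does not settle the matter, because SAP 2.3.2 contains both the restrictive sentence and the treated-patients rule.

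**2. Can the situation arise?** Yes, though the frequency is not given.
- One hematologic DLT in 8.5.3 requires Grade 4 neutropenia or thrombocytopenia to persist more than 7 days beyond the last dose. It can be met only after drug has stopped.
- Protocol 6.3 reports that 21 of 27 patients had discontinued, 13 of them for progression. It does not say how many stopped in Cycle 1.
- Protocol 12.5.1 collects AEs to 30 days after the last dose. Even a stop on Day 1 is covered to Day 31, so the event would normally be on record unless the subject has withdrawn consent to follow-up.

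**3. Effect on single decisions, if the event is left out and the subject replaced.**
- 2 of 3 (stop) becomes one scored DLT plus a replacement: expand if the replacement is DLT-free.
- 1 of 3 (expand) becomes none plus a replacement: escalate if the replacement is DLT-free.
- 2 of 6 (stop) becomes one plus a replacement: escalate if the replacement is DLT-free.
- 3 of 3 becomes two scored and still stops.

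**4. Illustration of size.** The documents state no operating characteristic for Part A, so there is no figure to reproduce. Two inputs are assumed: p, the true DLT rate at a level, and f, the share of DLTs that follow a stop for another reason.

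A level is cleared with 0 of 3, or with 1 of 3 followed by 0 of 3:

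P(clear) = (1−p)³ + 3p(1−p)²·(1−p)³ = (1−p)³ + 3p(1−p)⁵

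At p = 0.33: 0.3008 + 0.1337 = 0.434 (before rounding, 0.4344).

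A fraction pf of subjects is excluded and replaced, so the scored rate is p′ = p(1−f)/(1−pf). At p = 0.33 and f = 0.10: 0.297/0.967 = 0.3071, and P(clear) = 0.3326 + 0.1471 = 0.480.

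| p | f = 0 | 2% | 5% | 10% | 20% |
|---|---|---|---|---|---|
| 0.20 | 0.709 | 0.716 | 0.726 | 0.744 | 0.780 |
| 0.33 | 0.434 | 0.443 | 0.456 | 0.480 | 0.530 |
| 0.40 | 0.309 | 0.317 | 0.330 | 0.351 | 0.400 |

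**5. Sensitivity.** Suppose that 10% of DLT-free subjects also leave early and are replaced under either rule. The scored rate is then p(1−f)/(1−pf−0.1(1−p)). At p = 0.33, P(clear) is 0.390 with all DLTs counted, 0.434 at f = 10% and 0.485 at f = 20%. The increases, 0.045 and 0.096, are about the same as in the table.

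**The case against.** A reader might infer that the plan discards these DLTs and replaces the subjects. The documents do not support that. Four counting rules would include the event and only one sentence, read alone, would not. Replacement is discretionary in Protocol 9.3.1. The causal phrase also has an innocent source: Protocol 8.3.3 says that a Part A subject with a Cycle 1 DLT should be discontinued, and the evaluability sentence probably mirrors that. All of this stands, and it makes the finding a conflict rather than a settled exclusion.

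A reader might also infer that the MTD or the Part B dose has been biased upward. Nothing in the documents shows that any such event occurred or was left out. The safety review committee sees all AEs (Protocol 8.5.1) and can add subjects or stop escalation. Protocol 6.4.3 shows it weighing a Cycle 2 event, which lies outside the DLT window. A committee working that way is unlikely to ignore an event inside the window. This lowers the practical risk for escalation decisions, but it does not define the set on which the MTD is determined.

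Finally, no passage supports any particular share of DLTs arising after a stop for another reason. That is correct: the upper end of the illustration should not be read as an estimate.

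**Conclusion.** The point holds as an internal conflict. Taken literally, the evaluability sentence excludes a subject whose DLT falls inside the window after drug was stopped for another reason. The window and counting rules include that subject, and the replacement rules disagree with each other. No passage says which prevails.

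If the evaluability sentence is applied, the direction is clear: toward escalation and a higher MTD. The size is unknown. At an assumed true DLT rate of 0.33, the chance of clearing a level rises by about 1 to 2 percentage points if 2-5% of DLTs are unscored, and by about 5 to 10 points if 10-20% are. Both the rate and the share are assumptions, and the calculation supposes that every such subject is replaced and that no committee judgement intervenes. The correction is worth making because the ambiguity concerns a primary objective and is cheap to remove.

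**What to change.** In Protocol 8.5.2 and SAP 2.3.2, define the MTD-evaluable set as (a) every treated subject with a DLT in the DLT window, whatever the reason for stopping drug, and (b) subjects without a DLT who meet the existing 28-day drug requirement.

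Keep the exposure requirement in (b). If it were relaxed to mere follow-up through Day 28, a subject who stopped after a few days could count as DLT-free, which would itself favour escalation.

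Align Protocol 8.1, Protocol 9.3.1 and SAP 3.1 so that only subjects who leave Cycle 1 without a DLT in the window are replaceable, and so that replacement is described the same way in all three.

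The cost is one sentence in each document plus matching replacement text. The AE data are already collected. The rule can be applied to the up to 24 further Part A subjects (Protocol 8.2) and to the final MTD determination. It governs counting only and changes no dose, schedule or patient management.

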### 8.5.3 Dose-Limiting Toxicity (DLT) Definitions

During Phase 1, the MTD will be determined based on DLT occurring during the first 28 days plus any rest period if applicable (i.e. Cycle 1). All adverse events unless they have been determined to be not related to study drug will be taken into consideration in determining DLT. NCI-CTCAE version 4.03 will be the basis for the descriptive terminology and grading of adverse events. DLT are defined as follows:

#### **Non-hematologic DLT is defined as:**

Any Grade  $\geq 3$  AE, with the following exceptions

- Symptomatic adverse events such as nausea, vomiting and diarrhea will not be considered dose limiting if they can be reduced to less than grade 3 within 72 hours with standard supportive measures such as antiemetics and antidiarrheals.
- Asymptomatic Grade 3 electrolyte abnormalities which can be corrected by optimal supplementation.

**Hematologic DLT is defined as:**

≥ Grade 4 neutropenia or thrombocytopenia that lasts more than 7 days after the last dose of study drug;

Febrile neutropenia;

≥ Grade 3 thrombocytopenia in the presence of bleeding;

See section **12.4** for assessments of intensity criteria.

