### 3 SCHEDULE OF ASSESSMENTS

**Table 1: Schedule of Assessments (Part A)**

Study Procedure	Screening D (-28 to -1)	Cycle 1										Subsequent Cycles a				End of Treatment b	30-Day Follow- up		
		Days																	
		1	2	3	4	8	11	15	16	22	28	1	15	22	28				
Informed Consent	X																		
Eligibility Screening	X																		
Demographics	X																		
Medical History	X																		
Physical Examination c	X	X										X				X	X		
Disease History & Stage	X																		
Vital signs d	X	X	X	X		X		X	X	X		X	X			X	X		
Height e and weight	X	X										X				X	X		
ECOG PS	X	X										X				X			
12-lead ECG	X	X f	X	X		X		X f	X	X						X			
Pregnancy test, if applicable	X	X														X			
Serum Chemistry g	X	X				X		X					X			X	X		
Liver Function Tests g	X	X			X	X	X	X					X			X	X		
CBC with Diff and Platelets g	X	X				X		X					X			X	X		
Urinalysis g	X	X														X			
Disease Assessment h	X															X			
Medication Administration		X	X i	X	X								X	X					
Pharmacokinetic Sample		X	X j	X j		X j		X	X j	X j			X k						
Pharmacodynamic Sample		X				X		X					X l						
Adverse Events			X														X i		
Concomitant Medications	X															-X			
Dispense Drug Diary			X																
Medication Compliance						X		X			X		X			X			

a Subsequent cycles should begin within 3 days of either Day1, or the previous cycle. Subjects may continue to receive additional cycles of ASN002 in the absence of intolerable or severe toxicity or disease progression. All safety laboratory and radiographic evaluations for continued dosing must be completed prior to evaluation by the investigator.

b End of Treatment Visit should take place < 1 week from the last dose of study medication.

c Complete physical examination will be conducted at screening and end of treatment. Other examinations may be brief, problem-focused examinations and review of systems.

d Vital signs will consist of heart rate, blood pressure, and temperature. Day 3 and Day 16 apply to QD dosing cohorts only.

e Height to be obtained at baseline only.

f Refer to the Schedule of Assessments Table for Day 1, and Day 15. Day 3 and Day 16 apply to QD dosing cohorts only.

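### Part A's Grade 4 neutropenia/thrombocytopenia DLT criterion counts only time after the last dose, so under continuous dosing it misses cytopenia that reverses on stopping and can drop early stoppers from the MTD count

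*Protocol*

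**What the plan says.** Protocol 8.5.3 lists three hematologic DLT criteria. The first, introduced by a greater-than-or-equal sign, is "Grade 4 neutropenia or thrombocytopenia that lasts more than 7 days after the last dose of study drug". The synopsis and SAP 2.3.2 carry the same rule. The other two, febrile neutropenia and Grade 3 or higher thrombocytopenia with bleeding, have no duration test. The general criterion for Grade 3 or higher events stands under the non-hematologic heading, so it does not cover cytopenias.

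The surrounding rules are:

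- **Window (8.5.3):** "the MTD will be determined based on DLT occurring during the first 28 days plus any rest period if applicable". No rest period is scheduled.
- **Dosing (8.4):** BID subjects take drug twice daily from Day 2. QD subjects, on Day 3, "will begin continuous once daily dosing".
- **Evaluability (8.5.2):** the MTD count uses only subjects "who have received the study drug for 28 days or who have discontinued the study drug earlier than 28 days because of a DLT".
- **Stopping rule (8.5.2):** "The dose escalation will be stopped if 2 or more subjects among a cohort of 3 or 6 subjects experience a DLT".
- **Replacement:** 8.1 states "Subjects that are not able to complete Cycle 1 for reasons other than DLT will be replaced". In 9.3.1, a subject who leaves before completing 28 days "for reasons other than DLT, or has demonstrated significant non-compliance with ASN002 dosing, may be replaced at the discretion of the sponsor".
- **Later cycles (Table 1, footnote a):** "Subjects may continue to receive additional cycles of ASN002 in the absence of intolerable or severe toxicity or disease progression".
- **Dose modification (8.3.3, Part A):** no reductions, and discontinuation if a DLT occurs in Cycle 1. There is no separate instruction to hold drug for a Grade 4 count.

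**The concern.** A clock that starts at the last dose suits a regimen with a planned break. Part A has none, so time spent at Grade 4 while taking drug never counts. The criterion therefore measures how slowly counts recover off drug, and not how long the subject was severely cytopenic.

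That matters for this compound. Section 6.2 names bone marrow as a primary and reversible target. Section 6.3 describes hematologic changes as usually mild to moderate, but reports that severe neutropenia and thrombocytopenia have occurred and that white counts tended to move back toward baseline after treatment. Recovery on stopping is exactly the pattern an off-drug clock does not score.

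One event can decide a dose level, since 1 DLT in 6 lets it clear and 2 in 6 stop escalation. The question is still live: Section 6.4.4 continues dose finding in solid tumors, and Section 8.2 allows 24 more Part A subjects.

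**Working it through.** The plan gives no figure to reproduce, because Part A states no target DLT rate or operating characteristics. The check is to apply the rules as written to subjects without fever, bleeding or any other DLT.

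**1. When the criterion is met.** More than 7 days after the last dose means the eighth day after it.

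- Last dose on Day 28: 28 + 8 = Day 36. This falls in the DLT window only through the rest-period wording. Footnote a supports that route, because a subject still at Grade 4 should not start Cycle 2.
- To be met by Day 28 with no rest period, the last dose must fall on or before 28 − 8 = Day 20.

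**2. Two events with the last dose on Day 28 and Cycle 2 delayed.**

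| Grade 4 present | Calendar days | On drug | Off drug | Scored as DLT? |
|---|---|---|---|---|
| Days 8–35 | 35 − 8 + 1 = 28 | Days 8–28 = 21 | Days 29–35 = 7 | No |
| Days 28–36 | 36 − 28 + 1 = 9 | Day 28 = 1 | Days 29–36 = 8 | Yes |

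The longer event passes and the shorter one counts. A rule of more than 7 days, on or off drug, would score both.

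**3. A subject who stops early for good.** Suppose Grade 4 starts on Day 8, the last dose is on Day 15, and the count is below Grade 4 on Day 22.

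- Grade 4 lasts Days 8–21, which is 14 calendar days: 8 on drug (Days 8–15) and 6 off (Days 16–21).
- Six days off drug is not more than 7, so there is no DLT.
- The subject has not received drug for 28 days and did not stop because of a DLT, so neither route to evaluability in 8.5.2 applies.
- The subject will be replaced under 8.1, or may be under 9.3.1.

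**4. Effect on the decision.** If a level has one scored DLT among 6 evaluable subjects, one unscored event of either kind is the difference between 1 of 6 (clears) and 2 of 6 (stops). The error runs only toward escalation.

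**5. Whether another Part A rule closes the gap.** Section 8.3.3 discontinues a subject once a DLT has occurred in Cycle 1. This criterion cannot be met until drug has already been off for more than 7 days, so it cannot prompt the stop. Footnote a governs additional cycles, not days within Cycle 1.

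**6. How common the event might be.** Section 6.3 lists individual treatment-emergent events in more than 10% of 27 patients. Neutropenia and thrombocytopenia are not on the list. Since 3/27 = 11.1% would be listed and 2/27 = 7.4% would not, each was reported in at most 2 patients at any grade. This covers 10–75 mg BID and 80 mg QD at the February 2017 cutoff, and recorded adverse events only.

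**The case against.** The case for leaving the rule alone has substance.

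- **The event may be rare.** At most 2 of 27 patients had each cytopenia as a reported event. The word severe in Section 6.3 need not mean Grade 4, since Section 12.4 attaches it to Grade 3. Solid-tumor patients at 120 mg QD were treated for up to 4 cycles with no dose reduction needed (6.4.4). This stands, and it limits the weight of the point.
- **General safeguards exist.** Sections 8.1 and 8.4.2 allow treatment only while toxicity is tolerable, 9.3 permits discontinuation for an adverse event, and 12.4 says Grade 4 calls for urgent intervention. Twenty-one days of dosing through Grade 4 is therefore an extreme case. None of these is an explicit hold, however, and intolerable is not defined.
- **The committee can override.** It reviews all adverse events and laboratory data (8.5.1), and it weighed cumulative hematologic toxicity at 120 mg QD when it recommended 75 mg BID (6.4.3). This reduces the consequence but leaves the DLT count and the evaluability rule as they are.
- **A hold at onset would nearly repair the clock.** The last dose would then fall close to onset. That is right for the first gap. It does not help a subject who stops permanently and recovers within 7 days.
- **The data will be visible.** SAP 10.1 tabulates events by intensity, 10.2 lists drug-log data and 10.4 gives CTCAE shifts. Duration and dosing status are largely derivable from these.

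A reader might infer that subjects have already been misclassified, or that 75 mg BID is too high. The documents report no Grade 4 event and no replaced subject. Section 6.4.3 rests the dose on a pneumonia DLT, a pneumonitis SAE and the hematologic experience at 120 mg QD, not on this criterion. Nor can a change in escalation probability be quoted, because the documents give no Grade 4 rate or duration. The planned fed cohorts do not alter how the criterion counts.

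**Conclusion.** The point holds as a defect in the stated rule. Time at Grade 4 on drug is ignored, and a subject who stops permanently before Day 28 for Grade 4 cytopenia and recovers within 7 days is neither a DLT nor MTD-evaluable. The bias is toward escalation and its size is unknown.

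The conclusion rests on a literal reading of 8.5.2 and 8.5.3 and applies to afebrile, non-bleeding cytopenia. The evaluability part is limited to permanent discontinuation. For a short hold followed by resumption, 8.5.2 is unclear, and no loss of the subject is claimed.

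It should be fixed for the remaining Part A cohorts, because the change is specific and inexpensive. It does not by itself call past dose decisions into question. The Part A hold rule after Cycle 1 in 8.3.3 has a related wording problem: it waits for DLT criteria that this event meets only after more than 7 days off drug. That lies outside the MTD rule and is secondary.

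**What to change.** For the remaining Part A cohorts:

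1. **Duration.** In the synopsis, Protocol 8.5.3 and SAP 2.3.2, define the criterion as Grade 4 neutropenia or thrombocytopenia with onset in Cycle 1 that lasts more than 7 days, on or off study drug. For subjects with a Grade 4 value only, repeat the CBC until it is below Grade 4. If it has not recovered, include a draw at least 8 days after the first Grade 4 value, and keep the DLT call open until then. The visit text places laboratory draws on Days 8, 15, 22 and 29, so consecutive nominal draws are 7 days apart and cannot by themselves show more than 7.
2. **Early stoppers.** In Protocol 8.5.2 and 9.3.1 and SAP 2.3.2, count as a DLT any permanent Cycle 1 discontinuation because of Grade 4 neutropenia or thrombocytopenia, unless the event was determined to be unrelated to study drug. Such a subject is then MTD-evaluable and not replaceable. Align the replacement sentence in Protocol 8.1 and SAP 3.1 with this.

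Both documents must change, because Protocol Section 15 gives the SAP priority where they differ.

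Optionally, add to SAP 11.1 a by-dose listing of Cycle 1 Grade 4 neutropenia and thrombocytopenia with duration and dosing status, including the 40 subjects already enrolled.

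The cost is a wording amendment and a few extra blood counts. The drawbacks are that DLT criteria would differ from those applied to the 40 enrolled subjects and that more cohorts may expand to 6. The optional listing would show how much the mix matters, although past durations are known only to the interval between draws.
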